7.7.11 Interim Analysis

An interim analysis for futility will be conducted by an independent statistician. The sole purpose of the interim analysis is to help make a decision whether to continue the trial to the planned sample size, or to stop the trial for futility. No increase or decrease to the sample size will be performed, except to stop the trial for futility, therefore no adjustment to type-1 error is indicated. The interim analysis will be based on conditional power analysis when approximately 60 subjects (per group) have completed the double blind portion of the study. Only absolute lesion reduction count and IGA data (2 grade reduction, and Clear or Almost Clear (0, 1)) will be analyzed. The process for conducting the interim analysis and disseminating the recommendation to the sponsor will be described in the Statistical Analysis Plan. A charter will be written to describe in detail the process and roles related to this interim analysis. This charter will name the independent statistician to conduct the interim analysis, and the sponsor's designated personnel that will make final decisions.

7.7.12 Safety Analysis

Treatment emergent adverse events, and serious adverse events will be categorized by system organ class and Preferred Term from the current version of MedDRA. Treatment-emergent adverse events will be summarized overall, by severity, and by relationship to treatment. Changes from baseline in vital signs, laboratory parameters, immunogenicity parameters, and shifts from baseline laboratory parameters and in physical examinations will be summarized by treatment. All safety endpoints will be displayed for all treated subjects.

7.7.13 Week 16 (4 week follow-up) summary

Summary statistics for Week 16 study period will include baseline demographics, disposition, exposure, safety, and efficacy variables.

Efficacy summaries will include:

CONFIDENTIAL

Version Date: 10 July 2015

- The absolute change from baseline to Week 16 in inflammatory lesions (papules and pustules).
- IGA at Weeks 16: 2 point reduction; Clear or Almost Clear (IGA 0, 1).
- Percentage of subjects with an Investigator Assessment of Erythema (IAE) of clear or almost clear (0 or 1) at Week 16.
- Percentage of subjects with telangiectasia score of none or mild (0 or 1) at Week 16.
- Percentage of subjects with scaling/peeling score of none or mild (0 or 1) at Week 16.
- Percentage of subjects with pruritus score of none or mild (0 or 1) at Week 16.

Safety summaries will include:

- Concomitant medications
- Adverse events
- Vital signs and laboratory tests.

All efficacy and summaries will be performed by original double-blind randomized treatment group, and overall

7.7.14 Multicenter Analysis

Approximately 50 centers are planned in this study; whenever possible, approximately 16 subjects will be enrolled per center. In the event a center has a low (< 16) number of subjects enrolled or no subject that meets either of the IGA co-primary endpoints, pooling of centers may be performed based on geographical center location until the pooled center has at least 16 subjects and at least one subject with an IGA of clear or almost clear and at least one subject with a 2 point reduction in IGA.

Centers that do not meet above criteria will be pooled according to the following priorities:

1. Within a state/territory/country;
2. Across states/territory/country.

The exact pools will be determined prior to unblinding according to the above methodology.

Descriptive summary statistics will be generated including center and pooled-center (when appropriate) by co-primary and secondary efficacy endpoints.

8 ETHICS AND GENERAL STUDY CONDUCT CONSIDERATIONS

8.1 ETHICAL CONDUCT OF THE STUDY

This study will be conducted in accordance with the FDA and ICH guidelines on current GCP following the ethical principles originating from Declaration of Helsinki. Additionally, the study will be conducted in accordance with any applicable laws or regulations of the country in which the clinical research is conducted.

CONFIDENTIAL

Version Date: 10 July 2015

8.2 CHANGES IN STUDY CONDUCT/STATISTICAL ANALYSES/AMENDMENTS

No change in the conduct of the study should be instituted without written approval from the CRO/Sponsor. Substantial Amendments to the protocol require written approval from the Sponsor, Institutional Review Board, ethics committee and the regulatory authority, as applicable.

8.3 INSTITUTIONAL REVIEW BOARD (IRB) /INDEPENDENT ETHICS COMMITTEE (IEC)

This study, all appropriate amendments, all advertising, and written materials given to the subjects will be reviewed and approved by an Institutional Review Board/Independent Ethics Committee, prior to use.

8.4 SUBJECT INFORMATION AND CONSENT

The study personnel will inform all subjects in this study, in accordance with GCPs, about the study. The study personnel will review the informed consent form (ICF) with each subject and give the subject an opportunity to read the consent and have all questions answered before proceeding. A current written consent form, approved by an IRB/IEC, is to be supplied by the Investigator and willingly signed by each subject, prior to initiating any study procedures, including instructing the subject to discontinue the use of medications requiring wash-out. The Investigator is responsible for maintaining each subject's consent form in the study file and providing each subject with a copy of the signed form(s).

8.5 PROTOCOL ADHERENCE

The Investigator must read the protocol thoroughly and must follow the instructions exactly. Any change should be agreed upon by prior discussion between the CRO/Sponsor and the Investigator, with appropriate written protocol amendments made prior to implementation of the agreed-upon changes. Any amendment containing major modifications (particularly if it may involve an increased risk to the subjects) will be approved by the IRB/IEC before it may be implemented.

8.6 CONTRACTUAL REQUIREMENTS

A contractual agreement will be signed between the Sponsor/CRO and the Investigator/clinical site. This document will contain complementary information, i.e. financial agreement, confidentiality, study schedule, and publication of study results.

8.6.1 Publication Policy

All data generated from this study are the property of the Cutanea Life Sciences, Inc. Publication of data will be done in accordance with the contractual agreement between the Sponsor/CRO and Investigator/clinical site.

CONFIDENTIAL

Version Date: 10 July 2015

8.7 RECORD KEEPING

8.7.1 Data Collection

The Investigator must maintain detailed records on all study subjects. Data for this study will be recorded in the subject's chart and entered into eCRFs through the electronic data capture (eDC) system provided by the Sponsor's designated data management group. Applicable data from the subject's chart should be recorded in the eCRFs completely, promptly, and taking time to correct any mistakes as prompted by the eCRF system. Upon study completion or at any other time specified by the CRO/Sponsor, a monitor will review the appropriate eCRF pages.

Completed eCRFs should be ready for review by the CRO/Sponsor's Monitor, within one (1) week of each study visit for a given subject.

8.7.2 Data Corrections

Corrections of data entered into the eCRF must be made in the system for electronic case report forms, as appropriate.

- The CRO/Sponsor's Monitor will review the eCRFs, evaluate them for completeness and accuracy, and ensure that all appropriate information is entered.
- No changes will be made to the data on the eCRF pages after the data are determined to be final by the CRO/Sponsor's Monitor and data management group. Queries and comments may still be generated and answered on eCRFs as outlined in the eDC system.

8.7.3 Source Documentation

Investigators must keep accurate separate records (other than the eCRF) of all subjects' visits, which include all pertinent study-related information including the original signed/dated informed consent forms, and drug accountability records. As a minimum, a statement should be made in the subject's record indicating that the subjects have been enrolled in Protocol CLS001-CO-PR-005 and that they signed an informed consent form. Any adverse events must be thoroughly documented. Results of any diagnostic tests conducted during the study should also be included in the source documentation. Telephone conversations with the subjects and/or the CRO/Sponsor concerning the study must also be recorded.

8.7.4 Monitoring/Auditing

Representatives of the CRO/Sponsor, following GCP guidelines, will closely monitor the conduct of the study. In addition, inspections or on-site audits may be carried out by the local regulatory authority or by the CRO/Sponsor's independent Quality Assurance Department. The Investigator will allow the CRO/Sponsor's representatives and any regulatory agency to examine all study records, eCRFs, corresponding subject medical records, clinical drug dispensing records, drug storage area, and any other documents considered source documentation.

CONFIDENTIAL

Version Date: 10 July 2015

8.7.5 Archives

Records must be retained in accordance with the current ICH Guidelines on GCP. All essential study documents including records of subjects, source documents, eCRFs and study drug inventory must be kept on file.

Essential documents should be retained until at least 2 years after the last approval of a marketing application in the an ICH region and until there are no pending or contemplated marketing applications in an ICH region, or until at least 2 years have elapsed since the formal discontinuation of clinical development of the investigational products. However, essential documents may be retained for a longer period if required by the applicable regulatory requirements or by agreement with the Sponsor. The Sponsor is responsible for informing the Investigator when these documents need no longer be retained.

The Investigator will not dispose of any records relevant to this study without written permission from the Sponsor, and will provide the Sponsor the opportunity to collect such records. The Investigator shall take responsibility for maintaining adequate and accurate hard copy source documents of all observations and data generated during the study. Such documentation is subject to inspection by the Sponsor, its representatives, and regulatory authorities.

If the Principal Investigator retires, relocates, or for other reasons withdraws from the responsibility of keeping the study records, custody must be transferred to a person who will accept the responsibility. The CRO/Sponsor must be notified in writing of the name and address of the new custodian.

CONFIDENTIAL

Version Date: 10 July 2015

[REDACTED]

[REDACTED]

[REDACTED]

[REDACTED]

[REDACTED]

[REDACTED]

11 APPENDICES

APPENDIX A**Instructions On Application Of Study Drug**

You will apply study drug once daily, preferably in the morning.

Before applying the study drug:

1. Using a non-medicated soap or soapless cleanser, wash your hands and face at least 15 minutes before study drug is to be applied.
2. For the first dose, the study staff will review treatment application with you before you apply the study medication. The amount of product that you will apply each day should be a sufficient amount to cover your face with a thin layer of gel.

Application of the study gel:

1. Remove the cap from the study medication tube and squeeze a small line of product from the crease of your last knuckle to the tip of your finger (see picture below). The line should be approximately the width of the tip of the tube.

2. Next, apply the product in a thin layer by gently dabbing and blending it evenly over the entire face, including cheeks, chin, forehead and nose. Avoid contact with the corners of the eyes, mouth and inside the nose.
3. If additional product is needed to cover your face, then squeeze very small amounts of product from the tube and blend it evenly on the untreated areas of your face until your entire face has a thin film of product applied to it. If you notice dried or flaking product on your face, you may be applying too much product.
4. Return the cap to the study medication tube and store the tube of study medication at room temperature.
5. Record your treatment application on your diary
6. Keep clothing from contacting the treated areas until the gel dries.

You must not apply more than the recommended dose at any application.

- Showering/bathing (when you shower or bathe, use a non-medicated soap or soapless cleanser and wait at least 15 minutes prior to applying study drug).
- Males should shave at the same time every day, at least 15 minutes before study drug application.
- Wait until the gel is dry before applying makeup.
- Excessive exposure to the sun and tanning booths/beds should be avoided. Wait until the gel has dried before applying sun screen to your face. No new lotions, gels, powders, moisturizers, etc. and no topical medications should be used on the skin in the treatment areas.

Remember to bring your tube and diary back to the clinic at EVERY visit. Please call the clinic immediately if you have lost your tube.

Clinic Phone number: _____ Your next appointment is: _____

CONFIDENTIAL

Version Date: 10 July 2015

APPENDIX B

Fitzpatrick skin type classification:

- I: Always burn, never tan
- II: Usually burn, tan less than average (with difficulty)
- III: Sometimes mild burn, tan about average
- IV: Rarely burn, tan more than average (with ease)
- V: Rarely burns, tans profusely
- VI: Never burns, tans profusely

1. Fitzpatrick TB. The validity and practicality of sun-reactive skin types I through VI. Arch.Dermatol. 1988; 124: 869-871.
2. Sachdeva S. Fitzpatrick skin typing: Applications in dermatology. Indian J Dermatol Venereol Leprol 2009;75:93-6

CONFIDENTIAL

Version Date: 10 July 2015

## 1.0 Introduction

Rosacea is a chronic dermatologic disorder that primarily affects the facial skin. An estimated 16 million Americans have rosacea. The clinical signs and symptoms of rosacea are: facial flushing, telangiectasia, facial erythema, central facial inflammatory papules and pustules, hypertrophy of the sebaceous glands of the nose and ocular changes. Rosacea has been classified into four different subtypes; Subtype 1: erythematotelangiectatic, Subtype 2: papulopustular, Subtype 3: phymatous and Subtype 4: ocular. Each subtype has severity grades ranging from mild to severe.

Currently, there is no cure for rosacea and the etiology is poorly understood. Many theories regarding the cause of rosacea have been highlighted in the literature. The pathology of rosacea may be multifactorial: abnormal vascular and immune system responses; hair follicle mite *Demodex folliculorum*; bacteria such as *Helicobacter pylori*; prolonged steroid use and other aggravating trigger factors like sun and stress. Gallo and his colleagues found an abnormally high level of the naturally occurring antimicrobial peptide cathelicidins upon histopathological staining in the skin of patients with rosacea.

Cutanea Life Sciences is developing omiganan topical gel for the treatment of papulopustular rosacea. The exact cause of rosacea is unknown and may be in due in part to an inflammatory process. Recent research has shown that cationic peptides such as omiganan may have anti-inflammatory properties and may play a role in inhibiting the inflammatory response. Omiganan may also prevent the inflammatory cascade that is theorized to lead to the signs and symptoms of rosacea. A possible anti-inflammatory activity of omiganan is suggested by the observation of a reduction in inflammatory acne lesion counts with omiganan in two Phase 2 clinical trials. However, the exact mechanism of action is undetermined.

Two previous clinical studies of omiganan in rosacea were conducted. CLS001-R-001 was a double-blind, multicenter, randomized, vehicle-controlled, parallel group study in 240 adult subjects with subtype 2 papulopustular rosacea. Eligible subjects were randomized to 5 treatment groups in a 2:2:2:1:1 ratio. The treatment arms were Omiganan topical gel at 1% QD, 2.5% QD, 2.5% BID, and Vehicle QD and Vehicle BID. Subjects were treated for 9 weeks. In the Modified Intent-to-Treat (MITT) analysis, all efficacy variables improved compared with Baseline in all treatment groups. The reductions from Baseline tended to be greatest in the omiganan 2.5% QD group; however, there were no statistically significant differences between the active treatment groups and the combined vehicle group for any efficacy variable at the Week 9/end of treatment endpoint for the MITT population.

Based upon the results of the first Phase 2 study in rosacea, Cutanea determined that the dose-response relationship of omiganan warranted further exploration. An additional Phase 2B study CLS001-CO-PR-001 investigated the safety and efficacy of once-daily omiganan 1%, 1.75% and 2.5% compared to vehicle gel. Again this was a double-blind, multicenter, randomized, vehicle-controlled, parallel group study in 240 adult subjects with subtype 2 papulopustular rosacea. Subjects were randomized into 4 test groups at a 1:1:1:1 ratio and observed over the course of 12 weeks. In addition to the primary analysis of the change from baseline in inflammatory lesion counts for the Intent-to-Treat (ITT) population, several strata based on baseline lesion counts were also evaluated in post hoc analyses. The efficacy signal was improved with increasing baseline lesion count, and was best for the [REDACTED] omiganan treatment group.

## 2.0 Study Design

This study will be conducted as a double-blind, multicenter, randomized, vehicle-controlled, parallel group study at approximately 50 centers (whenever possible, about 16 subjects will be enrolled per center), involving 450 subjects with severe subtype 2, papulopustular rosacea. After giving informed consent, each subject will be screened for study eligibility according to specific inclusion/exclusion criteria. Eligible subjects will be randomized to one of two treatment groups in a 1:1 ratio. The treatment arms are either: omiganan (b) topical gel or vehicle once daily.

Omiganan or vehicle will be topically applied once daily to the entire facial area; cheeks, chin, forehead and nose, avoiding contact with the eyes, mouth, and inside the nose.

Following baseline testing and evaluation for acceptance into the study, the subjects will be supervised during the first test drug application on Day 1 to ensure that the study treatment is applied correctly. Thereafter, each subject will apply the study treatment at home (unsupervised) once daily for 12 weeks in the double-blind study period. Subjects will then continue in the follow-up period for an additional 4 weeks without treatment application. No concurrent rosacea therapy of any kind, especially over the counter antimicrobial soaps or soapless cleansers, prescription topical and/or systemic antibacterial agents, will be allowed during the course of the study. No changes in topical soaps should occur. Other concurrent therapies will be recorded throughout the study. Subjects will have scheduled office visits at Weeks 1, 3, 6, 9, and 12 (Final Visit). Additional Follow-up Visit will occur at Week 16 ( $\pm$  3 days).

## 3.0 Randomization

Subjects providing written informed consent and having met all inclusion and exclusion criteria will be randomized to 1 of 2 treatment groups in a 1:1 ratio during the double-blind portion of the study, according to a predetermined computer-generated randomization code.

Subjects will be randomized to treatment using an Interactive Web Response System (IWRS). The randomization scheme will include investigative center. The randomization will be performed using permuted blocks.

## 4.0 Study Objective

The objective of this study is to evaluate the safety and efficacy of once-daily topical application of omiganan (b) topical gel compared to vehicle gel in subjects with severe papulopustular rosacea (IGA Grade 4 with baseline inflammatory lesion count  $\geq$  30).

## 5.0 Statistical Methodology

All statistical analyses will be performed using SAS® software version 9.3. Unless otherwise specified, all statistical tests will be two-sided with a significance level of 0.05. Continuous parameters will be summarized by N (number of non-missing observations), mean, standard deviation, median, minimum, and maximum. Categorical parameters will be summarized by count and percent.

### **5.1 Sample Size Determination**

The primary objective of the study is to show superiority of Omiganan [REDACTED] over vehicle for the treatment of rosacea in patients with severe papulopustular rosacea (IGA Grade 4 with baseline inflammatory lesion count  $\geq 30$ ). A sample size calculation was made for two co-primary endpoints. For change from baseline in inflammatory lesions, it is assumed that in the Omiganan [REDACTED] treatment arm, subjects will have an average reduction of 13.5 inflammatory lesions, compared to 4 in the vehicle arm. The standard deviation is assumed to be 12. For 95% power, a sample size of 86 subjects (43 per group) is needed. For Investigator Global Assessment (IGA), it is assumed that Clear or Almost Clear (IGA of 0 or 1) at Week 12 has a lesser power than 2 point reduction. It is also assumed that 17% of the subjects in the Omiganan [REDACTED] treatment arm versus 6% in the vehicle arm will have IGA of clear or almost clear at Week 12. For 95% power and using a Fisher's Exact test, 450 subjects (225 in each arm) are needed. Therefore, the number of subjects needed to ensure at least 95% power for both endpoints is 450.

The sample sizes were calculated using 95% power in order to ensure 90% power across two Phase 3 studies.

### **5.2 Analysis Populations**

The "Intent-to-Treat" (ITT) analysis population will include all randomized subjects. The ITT population will be the primary population for all efficacy analyses. Subjects will be analyzed based on the randomized treatment group, regardless of the treatment actually received.

The "All-Treated" analysis population will consist of all subjects receiving at least one application of study medication. All safety analyses will be performed on the all-treated population. Subjects will be analyzed based on the treatment actually received, regardless of the treatment group to which they were randomized.

### **5.3 Efficacy Endpoints**

The co-primary endpoints are:

- The absolute change from baseline to Week 12 in inflammatory lesions (papules and pustules).
- IGA at Week 12: 2 point reduction; Clear or Almost Clear (IGA 0, 1).

Secondary endpoints are:

- The absolute change from baseline to Week 9 in inflammatory lesions (papules and pustules).
- The absolute change from baseline to Week 6 in inflammatory lesions (papules and pustules).
- IGA at Week 9: 2 point reduction; Clear or Almost Clear (IGA 0, 1).
- IGA at Week 6: 2 point reduction; Clear or Almost Clear (IGA 0, 1).

Exploratory endpoints:

- The absolute change from baseline to Weeks 1 and 3 in inflammatory lesions (papules and pustules).
- Percentage of subjects with an IGA of clear or almost clear (0 or 1) at Weeks 1 and 3.
- Percentage of subjects with a 2 point IGA reduction at Weeks 1 and 3.
- Percentage of subjects with an Investigators Assessment of Erythema (IAE) of clear or almost clear (0 or 1) at each visit.
- Percentage of subjects with telangiectasia score of none or mild (0 or 1) at each visit.
- Percentage of subjects with scaling/peeling score of none or mild (0 or 1) at each visit.
- Percentage of subjects with pruritus score of none or mild (0 or 1) at each visit.

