7.2 SELECTION OF STUDY POPULATION

7.2.1 Inclusion Criteria

Subjects must meet each of the following criteria to be considered eligible for entry into the study:

1. Subjects who provided written informed consent to participate in the study.
2. Healthy, male and non-pregnant female subjects, 18 years of age or older.
3. A diagnosis of papulopustular rosacea with ≥ 30 inflammatory facial lesions (papules, pustules) at Baseline. Subjects must have no more than 2 nodular lesions, at Baseline.
4. Subjects with the presence of telangiectasia at Baseline.
5. Subjects with an erythema score of at least 2 on the Investigator Assessment of Erythema (IAE) scale at Baseline.
6. Subjects with a grade 4 (severe rosacea) on the 5-point Investigators Global Assessment (IGA) scale at Baseline.
7. Non-nursing, female subjects of child bearing potential, who are using a highly effective form of birth control or females not of childbearing potential due to menopause (must be postmenopausal for at least one year).
 - Highly effective methods of birth control are defined as those, alone or in combination, that result in a low failure rate (i.e. less than 1% per year) when used consistently and correctly. Forms of birth control include: Oral (birth control pills), Intravaginal: (e.g. NuvaRing®), Implantable (e.g. Norplant®), injectable (e.g. Depo-Provera®) or transdermal (e.g. Ortho Evra®) contraception; intrauterine device (IUD); double-barrier (diaphragm or condom with spermicidal gel or foam); for two months prior to study enrollment (see exclusion criteria #6) or a vasectomized partner or true abstinence (in line with preferred and usual lifestyle of subject) with an acceptable form of birth control should the subject become sexually active. Periodic abstinence (e.g., calendar, ovulation, symptothermal, post-ovulation methods) and withdrawal are not acceptable methods of contraception. All female subjects of child bearing potential must undergo an in-office, highly sensitive urine pregnancy test, with a negative result, prior to being randomized to receive study drug. In addition, women of childbearing potential must agree to have a highly sensitive urine pregnancy test at the end of the study.
8. Subjects who have used the same brand of soap, make-up, hair products, or shaving lotion/foam/cream/gel for a period of at least four weeks prior to the Baseline Visit and agree not to change these product brand/types during the study.

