7.4 EFFICACY VARIABLES

The efficacy evaluations should be performed by the Principal Investigator or appropriately qualified Sub-Investigator. The same evaluator should perform the Investigators Global Assessments (IGA), the Investigators Assessment of Erythema (IAEs), Other Signs and Symptoms Assessment and the lesion counts, (see Sections 7.4.1, 7.4.2, 7.4.3, and 7.4.4) for the same subject at each visit. **It is important that the same evaluator performs the Investigator assessments and lesion count for the same subject at each visit, however it may not be feasible in all instances. Every effort should be made to maintain consistency of the evaluator for each subject.**

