7.4.2 Investigators Assessment of Erythema (IAE)

The IAE should be performed at screening and each visit (Baseline, Weeks 1, 3, 6, 9, 12, and 16) prior to performing the lesion count using the scale below. The IAE is intended for the global evaluation of erythema of rosacea. This is an assessment of nontransient erythema, or background erythema. Telangiectasias are assessed separately as described under section 7.4.3.

Investigators Assessment of Erythema (IAE) Scale

Grade	Grading Scale Score	Description of Background Erythema
Clear	0	No redness present. Background erythema is consistent with non-involved areas.
Almost Clear	1	Slight and localized background erythema in involved areas of the face, usually limited to the malar prominence of the cheeks. Gives the impression of a healthy glow to the cheeks.
Mild	2	Slight to mild background erythema NOT limited just to the cheeks, but extends to the lateral cheeks, chin, or forehead.
Moderate	3	Definite background redness, easily recognized, and extending to lateral cheeks, chin, or forehead.
Severe	4	Severe background erythema over the entire face.

The IAE rating of erythema is considered as part of the baseline assessment. If a worsening of erythema from Baseline is believed by the investigator to be related to the study drug and not the disease, then it should be recorded as an AE.

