### 5.4.2 Efficacy Analysis

The co-primary endpoint of absolute change from baseline in inflammatory lesions will be analyzed using an Analysis of Covariance (ANCOVA) model, with treatment as a main effect, and pooled center as a covariate. To investigate consistency of efficacy results across study centers, treatment by center interaction will be tested at 0.1 level of significance and, if significant, it will be further be explored.

No adjustments will be made for multiple comparisons of efficacy endpoints. All analyses will be considered exploratory in nature due to the discontinuation of enrollment following the interim analysis.

Both IGA endpoints will be analyzed using a Cochran–Mantel–Haenszel (CMH) test, with center as the stratification factor. If the overall IGA response rates are less than 10%, a Fisher’s Exact test will be used to corroborate the CMH test. All tests of the co-primary endpoints will be analyzed.

For all efficacy analyses, small centers may be pooled in order to ensure sufficient cell counts for statistical testing.

Subgroup summaries (e.g. Gender, Age, Race, and Center) of the co-primary endpoints will be performed

[figure not shown]

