#### **5.4.5 Week 16 (4 Week Follow-Up) Summary**

Summary statistics for Week 16 study period will include baseline demographics, disposition, exposure, safety, and efficacy variables.

Efficacy summaries will include:

- The absolute change from baseline to Week 16 in inflammatory lesions (papules and pustules).
- IGA at Weeks 16: 2 point reduction; Clear or Almost Clear (IGA 0, 1).
- Percentage of subjects with an Investigator Assessment of Erythema (IAE) of clear or almost clear (0 or 1) at Week 16.
- Percentage of subjects with telangiectasia score of none or mild (0 or 1) at Week 16.
- Percentage of subjects with scaling/peeling score of none or mild (0 or 1) at Week 16.
- Percentage of subjects with pruritus score of none or mild (0 or 1) at Week 16.

Safety summaries will include:

- concomitant medications
- adverse events that were emergent during the follow-up study period
- vital signs and laboratory tests.

All Week 16 summaries will be performed by original double-blind randomized treatment group, and overall.

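### The only erythema efficacy result, IAE 0 or 1, asks for a one-, two- or three-grade fall depending on entry grade, and no planned analysis uses Baseline IAE

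*SAP*

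**What the plan says.** Among the exploratory endpoints, SAP section 5.3 lists "Percentage of subjects with an Investigators Assessment of Erythema (IAE) of clear or almost clear (0 or 1) at each visit". Section 5.4.5 adds the follow-up version, "Percentage of subjects with an Investigator Assessment of Erythema (IAE) of clear or almost clear (0 or 1) at Week 16". Protocol sections 7.7.6.3 and 7.7.13 match. No other erythema efficacy summary appears in either document.

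The entry rule in Protocol 7.2.1 is "Subjects with an erythema score of at least 2 on the Investigator Assessment of Erythema (IAE) scale at Baseline".

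Protocol 7.4.2 describes the two grades on either side of the cut. Grade 1, the highest that counts as response, is "Slight and localized background erythema in involved areas of the face, usually limited to the malar prominence of the cheeks". Grade 2, the lowest that is eligible, is "Slight to mild background erythema NOT limited just to the cheeks, but extends to the lateral cheeks, chin, or forehead".

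SAP section 5.4.2 gives an ANCOVA for the lesion count and a CMH test for IGA. It gives neither a model nor a test for IAE. It also states: "All analyses will be considered exploratory in nature due to the discontinuation of enrollment following the interim analysis". On assessment, Protocol 7.4 says "Every effort should be made to maintain consistency of the evaluator for each subject", while accepting that one evaluator throughout may not always be possible.

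**The concern.** Response begins at the grade next to the entry cut, and grades 1 and 2 differ mainly in how far slight redness spreads. A grade 2 entrant read as grade 1 at a later visit is a responder. A grade 4 entrant who falls to grade 2 is not. One percentage therefore pools three different amounts of change, in proportions set by the baseline mix.

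Because subjects are selected on a Baseline reading of 2 or more, some with true severity near the boundary enter on a high reading and later read lower. That is regression to the mean, and it gives a response rate above zero without any change in erythema.

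What is at stake is the readability of the trial's only erythema result. A percentage quoted for one arm cannot be separated from grading noise, and the comparison between arms discards most of a five-point scale and all of the Baseline information.

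**Working it through.** **Figures in the plan.** The documents give no expected IAE rate, baseline IAE distribution or grading error, so there is no IAE figure to reproduce. The two stated sample sizes do reproduce and do not depend on IAE:
- Lesions: 2 × (1.96 + 1.645)² × 12² / 9.5² = 41.5, so 42 per arm. The t-test version needs 42.5, so 43 per arm and 86 in all.
- IGA 0/1, 17% v 6%: exact two-sided Fisher power at 225 per arm is 95.1%.

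**Step 1: what the cut asks for (no assumptions).** Fall needed to reach grade 1:

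| Baseline IAE | Fall needed | Result at grade 2 |
|---|---|---|
| 2 | 1 | no change |
| 3 | 2 | non-responder after a 1-grade fall |
| 4 | 3 | non-responder after a 2-grade fall |

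**Step 2: response with no true change, simple form.** Rate = f2 × q, where f2 is the share entering at grade 2 and q is the chance that such a subject is later read as 1 or lower. Both are assumed. With f2 of 10 to 70% and q of 5 to 30%, the rate runs from 0.10 × 0.05 = 0.5% to 0.70 × 0.30 = 21%. A value near 5% needs, for example, 0.50 × 0.10 or 0.20 × 0.25.

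**Step 3: the same with a latent model.** Assume stable latent severity with SD 0.7 and independent reading error at each visit. Readings are rounded to 0–4, subjects with a Baseline reading of at least 2 are kept, and later readings of 1 or less are counted (2,000,000 simulated subjects per scenario).

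| Latent mean | Error SD | Response with no change |
|---|---|---|
| 2.3 | 0.3–0.5 | 6.0–10.4% |
| 2.6 | 0.2 | 2.1% |
| 2.6 | 0.3–0.5 | 3.3–6.3% |
| 2.9 | 0.3–0.5 | 1.6–3.5% |

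Over means 2.3 to 2.9 and error SD 0.2 to 0.5, the range is about 1 to 10%. At mean 2.6, error SD 0.3 to 0.5 means exact repeat agreement of about 67 to 50%. With error SD 0.3 to 0.5, grade 2 entrants respond at 6 to 18%, grade 3 entrants at 3.5% or less and grade 4 entrants at 0.3% or less. About 80 to 99% of these responders entered at grade 2.

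**Step 4: power for an assumed 0.4-grade benefit.** Take latent mean 2.6, SD 0.7, error SD 0.45 and an illustrative 60 per arm. From SAP section 5.0, "all statistical tests will be two-sided with a significance level of 0.05".

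- IAE 0/1: the model gives about 15% active v 5.5% vehicle, average 10.25%. SE = √(2 × 0.1025 × 0.8975 / 60) = 0.0554. Power ≈ Φ(0.095/0.0554 − 1.96) = Φ(−0.245) ≈ 40%. Simulation gives 39%.
- Baseline-adjusted score: variance of one reading ≈ 0.49 + 0.2025 + 0.0833 (rounding) = 0.7758. Residual variance ≈ 0.7758 − 0.49²/0.7758 = 0.466, so SD 0.683. SE = 0.683 × √(2/60) = 0.1247. Power ≈ Φ(0.4/0.1247 − 1.96) = Φ(1.25) ≈ 89%. Simulation gives about 88%.

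With mean 2.3 or 2.9 and error SD 0.3 or 0.5, simulated power is 27 to 62% for 0/1 and 82 to 98% for the adjusted score. With no effect, neither analysis rejects more than about 5% of the time.

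**The case against.** The best defence is that little depends on this endpoint. It is exploratory, the SAP calls every analysis exploratory, and no IAE test is planned, so the power comparison has no specified test to attach to. Reaching clear or almost clear is an attained state, and ignoring partial improvement is part of such a definition. IGA 0/1 does the same to a subject who goes from 4 to 2. The 0.4-grade benefit is assumed, and 60 per arm is the interim trigger rather than a stated final size. At the planned 225 per arm, the 0/1 comparison would have about 92% power in the same setting. All of this stands. It limits the weight of the point but does not remove the uneven requirement or the unused Baseline grade.

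A reader might also be tempted by four stronger readings that the documents do not support:
- **That a fixed share, such as 5%, responds from noise.** No repeatability or baseline mix is given, so only an assumed range can be stated. Keeping the same evaluator where feasible would push towards its lower end.
- **That no minimum change is required.** The two cuts together force at least a one-grade fall for every eligible subject.
- **That improvement from grades 3 and 4 is lost altogether.** Falls from 3 to 1 and from 4 to 1 both count.
- **That the treatment comparison is biased.** The trial is randomised, double-blind and vehicle-controlled, so noise and regression to the mean act on both arms alike.

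**Conclusion.** The point holds as a modest weakness in an exploratory endpoint. It follows from the text alone that one cut asks for one, two or three grades depending on entry, and that Baseline IAE is never used in an erythema analysis.

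The size rests on assumptions. About 1 to 10% of subjects would reach 0 or 1 with no true change under the latent model with mean 2.3 to 2.9, SD 0.7 and error SD 0.2 to 0.5, and most of them would come from grade 2. The effect is to dilute the comparison and to make single-arm rates hard to interpret. It does not create a false difference, and the co-primary endpoints and the sample size are untouched.

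The point is still worth acting on. Enrolment stopped after the interim analysis, so the erythema data will be read descriptively from fewer subjects than planned, where losing information costs more.

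**What to change.** In SAP sections 5.3, 5.4.2 and 5.4.5:

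1. Add an erythema comparison of IAE grade at each visit, including Week 16, adjusted for Baseline IAE grade. Use either ANCOVA on the score or a CMH row-mean-score test stratified by Baseline IAE.
2. Keep the percentage at IAE 0 or 1 as descriptive, and tabulate it by Baseline IAE grade (2, 3, 4) within each arm, so that one-grade crossings from grade 2 can be seen.

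Replacing the definition with a minimum two-grade fall, or requiring 0 or 1 at two visits, is not advised. Both reduce noise responders, but in the Step 4 setting power drops from 39% to about 10% and 27% respectively.

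The cost is one model and one table on data already collected at every visit. No multiplicity scheme is disturbed, because SAP section 7.0 removed those adjustments. The downside is that a mean grade difference is less intuitive than a percentage, which is why the percentage stays.
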